2.3.5. Data Safety and Monitoring Committee

An independent Data Safety and Monitoring Committee (DSMC), comprising experts in haematology, infectious diseases and statistics will be established before patient enrolment. The DSMC will be responsible for safeguarding the interests of trial participants and assessing the safety and efficacy of the trial. The DSMC will monitor evidence for treatment harm and compliance with the protocol. The DSMC will be advisory to the ITSC. The ITSC will be responsible for promptly reviewing the DSMC recommendations, to decide whether to continue or discontinue treatments within a domain, and to determine whether amendments to the protocol or changes in trial conduct are required.

The DSMC will be guided by a DSMC Charter that delineates the roles and responsibilities of the DSMC, including lines of communication between trial investigators, trial data coordinating centre, and Monash University.

2.3.6. Role of the Sponsor

Monash University plays a lead role in the design and central management of this trial. Monash University will have ultimate authority over the trial design; collection, management, analysis, and interpretation of data; writing of the report; or the decision to submit the report for publication. Monash University is the sponsor of the trial in Australia.

The Platform can have multiple regional Sponsors. Sponsors are organisations that take overall responsibility of the conduct, governance and insurance of the trial in a defined region. The role of the Sponsor in each region is specified in each RSA.

[figure not shown]
2.3.7. Role of trial funder(s)

The Australian National Health and Medical Research Council (NHMRC) and Medical Research Future Fund (MRFF) are the initial funders of the platform. The funders have no role in the design of the trial and will not have any role during its execution, analyses, interpretation of the data, or decision to submit results for presentation or publication.

2.4. TRIAL DESIGN

This trial is an investigator-initiated open-label, randomised controlled adaptive platform trial open in multiple sites. The platform design allows many treatment approaches to be tested simultaneously, and for pre-specified interim analyses that can be used to stop recruitment early to arms showing insufficient evidence of efficacy or overwhelming evidence of efficacy. The overview of the platform is shown in Figure 3. Participants who have enrolled in and completed one domain may be rotated and invited to participate in another domain appropriate to their changed status and subject to meeting domain-specific eligibility criteria.

Figure 3: Overview of trial platform

3. AIMS AND OUTCOMES

3.1. AIMS

The primary aim of this platform trial is, for patients with haematological malignancies, to determine the optimal supportive care interventions.

3.2. OUTCOMES

3.2.1. Primary outcome

Event-free survival (EFS), defined as time from randomisation (or, in domains with a single treatment arm, time from registration) until occurrence of a Grade 3 or higher infection (as defined by CTCAE Version 5), or death from any cause.

This is the primary outcome for trial results for each domain, unless otherwise specified in the Domain Specific Appendix.

3.2.2. Secondary outcomes

1. Occurrence of at least 1 Grade 3 or higher infection(s) from randomisation to 12 months.
2. Occurrence of one or more clinically documented infections (symptoms/signs of infection requiring antimicrobial treatment) from randomisation to 12 months.
3. Number of clinically documented infections (symptoms/signs of infection requiring antimicrobial treatment) from randomisation to 12 months.
4. Occurrence of one or more microbiologically documented infections from randomisation to 12 months.
5. Number of microbiologically documented infections from randomisation to 12 months.
6. All-cause mortality at 12 months
7. Infection-related mortality at 12 months

8. Time free from hospitalisation with antimicrobial administration with therapeutic intent from randomisation to 12 months.
9. Occurrence of one or more treatment-related adverse events
10. Number of treatment-related adverse events.
11. Isolation of fluoroquinolone resistant organisms, co-trimoxazole resistant organisms, extended spectrum beta lactamases or multidrug resistant organisms from randomisation to 12 months.
12. Number of infections with fluoroquinolone resistant organisms, co-trimoxazole resistant organisms, extended spectrum beta lactamases or multidrug resistant organisms isolated from randomisation to 12 months
13. QoL measured at randomisation, 3, 6, 9 and 12 months (EQ-5D-5L, EORTC QLQ-30 and FACT-N.).
14. Costs associated with allocated treatment arm and infections during study.

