4.5.4. Blinding

Acknowledging the difficulty in blinding to regular administration of parenteral immunoglobulin replacement, the current standard of care in many regions, treatments will be provided on an open-label basis, unless otherwise specified in the DSA. Where interventions are conducted on an open-label basis, all members of the ITSC will remain blinded to aggregate reports until a platform conclusion is reported by the DSMC.

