6.1.2. Adverse Reaction (AR)

Any untoward and unintended response to an investigational medicinal product related to any dose administered. All adverse events judged by either the reporting investigator or the sponsor as having a reasonable possibility of a causal relationship to an investigational medicinal product would qualify as adverse reactions. A causal relationship between the trial treatment (or medication error, misuse/abuse of medicinal product) and an adverse event occurs where there is at least a reasonable possibility that the trial treatment caused the event, i.e. the relationship cannot be ruled out.

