6.2. Adverse event reporting

6.2.1. All Adverse Events (AEs)

All AEs that occur between the first trial-related procedure (i.e. screening) and 30 days following end of domain intervention must be recorded on the AE log.

Investigators must record their opinion concerning details of the nature, onset, duration and severity of the AE, and assess any relationship to the trial intervention. Assessment criteria are defined below. **Severity**

Severity for each adverse event, including any lab abnormality, will be determined by the Investigator using the Common Terminology Criteria for Adverse Events v5.0 (CTCAE) as a guideline, wherever possible. In those cases where the CTCAE criteria do not apply and where there is no accepted alternative grading system, severity should be defined according to the following criteria:

Mild	Awareness of sign or symptom, but easily tolerated
Moderate	Discomfort enough to cause interference with normal daily activities
Severe	Inability to perform normal daily activities

Life-threatening Immediate risk of death from the reaction as it occurred.

Causality

Relationship to trial treatment will be determined by the Investigator as follows:

Unrelated	No relationship between the experience and the administration of the trial treatment; related to other aetiologies such as concomitant medications or participant's clinical state
Unlikely	The current state of knowledge indicates that the relationship is unlikely
Possibly related	Temporal association, but other aetiologies are likely to be the cause
Probably related	Temporal association, other aetiologies are possible but unlikely
Related	Established temporal or other association and event not reasonably explained by the participant's known clinical state or other modes of therapy administered

Expectedness

An expectedness assessment needs to be conducted for all SAEs by the Sponsor with regard to the trial intervention, using the appropriate investigator brochure or treatment information.

Expected	The event is listed in the investigator brochure or the trial protocol as expected with the trial treatment or is commonly seen in clinical experience (patient population, dosage).
Unexpected	The event is not listed in the investigator brochure or in the trial protocol, or the severity of the event is greater than that listed in the investigator brochure or the trial protocol.

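### The only adverse-event outcomes in the core list count investigator-attributed events, so they are not comparable between a drug arm and a cessation or no-drug arm

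*Protocol*

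**What the plan says.** - **Outcomes.** Section 3.2.2 has two adverse-event outcomes: number 9, "Occurrence of one or more treatment-related adverse events", and number 10, "Number of treatment-related adverse events". No all-cause adverse-event outcome and no serious-adverse-event outcome is listed. Outcomes 1 to 5, 8, 11 and 12 run from randomisation to 12 months, and 6 and 7 are set at 12 months. Outcomes 9 and 10 state no window.
- **Who decides.** Section 6.2.1: "Relationship to trial treatment will be determined by the Investigator as follows". Its lowest level, Unrelated, begins "No relationship between the experience and the administration of the trial treatment". Section 6.3, on the serious-adverse-event form, asks instead about relatedness to the assigned intervention.
- **Blinding.** Section 4.5.4: "treatments will be provided on an open-label basis, unless otherwise specified in the DSA". The adjudication committee in section 4.6 works blinded to arm, but its listed tasks are infection outcomes and infection-related mortality.
- **Threshold.** Section 6.1.2 accepts a causal relationship when there is at least a reasonable possibility, "i.e. the relationship cannot be ruled out". Section 6.2.1 has an Unlikely level and defines Possibly related as "Temporal association, but other aetiologies are likely to be the cause".
- **Setting.** Section 2.1.3 names the time to stop immunoglobulin replacement as one of the platform's questions. The arms themselves are left to the Domain-Specific Appendices.

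**The concern.** An attributed event needs something to be attributed to. On the section 6.2.1 wording, a participant who receives no drug can hardly have a treatment-related event, whatever happens to them. A participant on immunoglobulin or antibiotics can have one whenever an investigator who knows the allocation suspects the drug. A between-arm difference in outcomes 9 and 10 then mixes true toxicity with knowledge of the arm, and it leaves out whatever non-infective harm occurs off drug.

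The practical risk is that outcomes 9 and 10 are reported as the adverse-event comparison for a cessation question and read as showing which strategy causes fewer adverse events overall. They cannot show that. The Protocol treats this comparison as worth having: section 2.1.1.3 names adverse effects among the unknowns when immunoglobulin is compared with other options.

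**Working it through.** The Protocol states no sample size, error rate, power or adverse-event rate, so there is no figure to reproduce. The check has two parts.

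**1. Which harms are counted without a causality label?**

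- Serious infection or death: yes, through event-free survival (3.2.1) and secondary outcomes 1, 6 and 7.
- Hospital stay: only when antimicrobials are given with therapeutic intent (outcome 8).
- Resistant organisms and quality of life: yes (11, 12 and 13).
- Non-fatal, non-infective serious event: no. It is counted as an event only through outcomes 9 and 10, and so only if the investigator attributes it to treatment.

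Section 2.1.1.2 says that immunoglobulin side-effects can occasionally be serious, and the paper it cites concerns thromboembolic events in patients with haematological malignancy. Such events have other possible causes in this population. Whether one counts therefore depends on the investigator's judgement and on where the cut is made between sections 6.1.2 and 6.2.1.

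**2. How far could the attribution rule move outcome 9?**

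All inputs here are assumptions: n = 100 per arm, two-sided 5% test, all-cause risk P, and share f of that risk labelled related.

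Outcome 9 risk: p = P × f in each arm.

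Probability of a significant result = Φ[(d − 1.96 × se0) / se1], where d = |p1 − p2|, pbar = (p1 + p2)/2, se0 = √(pbar(1 − pbar) × 2/n) and se1 = √(p1(1 − p1)/n + p2(1 − p2)/n).

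Worked case, equal true risk: p1 = 0.50 × 0.20 = 0.10 on drug and p2 = 0.50 × 0.02 = 0.01 off drug. Then d = 0.09, pbar = 0.055, se0 = √(0.055 × 0.945 × 0.02) = 0.0322 and se1 = √(0.0009 + 0.000099) = 0.0316. The result is Φ[(0.09 − 0.0632)/0.0316] = Φ(0.85) = 0.80.

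| All-cause risk, on / off drug | Share labelled, on / off | Outcome 9, on / off | Off minus on (points) | P(significant, favouring no drug) |
|---|---|---|---|---|
| 50% / 50% | 10% / 5% | 5% / 2.5% | −2.5 | 0.15 |
| 50% / 50% | 20% / 2% | 10% / 1% | −9 | 0.80 |
| 50% / 50% | 40% / 0% | 20% / 0% | −20 | 1.00 |
| 50% / 70% | 10% / 5% | 5% / 3.5% | −1.5 | 0.08 |
| 50% / 70% | 20% / 2% | 10% / 1.4% | −8.6 | 0.75 |
| 50% / 70% | 40% / 0% | 20% / 0% | −20 | 1.00 |

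In the last three rows the no-drug arm truly has 20 points more all-cause events, yet outcome 9 still favours it by 1.5 to 20 points. An all-cause comparison shows a difference of 0 for 50% versus 50%. For 50% versus 70% it shows +20 points against no drug, with power 0.83 (0.29 for 50% versus 60%). The formula is a normal approximation and is rough when a risk is near zero. The platform's own analyses are Bayesian. The table shows direction and order of size only.

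**The case against.** - **Harm is measured elsewhere.** A reader might infer that outcomes 9 and 10 are the trial's only safety outcomes and that it could not detect net harm from stopping. The documents do not support that. The main expected harm of stopping immunoglobulin is serious infection or death, and the primary outcome counts exactly those without attribution. Mortality, resistance and quality of life add to it. This objection stands in full. The gap is confined to non-fatal, non-infective events.
- **The no-drug arm is inferred.** The core Protocol defines no arms. The Domain-Specific Appendices are not at hand; they may give a stopping strategy an active drug, add outcomes (2.2.2) or change the blinding (4.5.4). This stands, so the point is conditional on such a domain.
- **Zero is not fixed by the text.** A reader might infer that a no-drug arm scores zero by definition. Section 6.2.1 points that way, but the assigned intervention in section 6.3 could be read to include assigned cessation. The two sections need reconciling.
- **The difference may be true toxicity.** If treated participants have related events and untreated ones have none, outcome 9 may be doing its job. Equal all-cause risk with unequal labelling requires misattribution or offsetting harms, and neither is shown. This is fair: the table shows what the definition permits, not what will happen.
- **All-cause data exist.** Section 6.2.1 logs every adverse event with severity, section 1.2 schedules review at every visit, and section 6.3.4 sends reports to the monitoring committee. All-cause tables and the choice of causality levels are often left to the analysis plan. This stands in part: silence on the causality levels alone would be no finding. But the Protocol does fix the outcome definition itself as attribution-dependent, and committee monitoring is not a reported between-arm outcome.
- **Aim.** A reader might take the comparison of benefits, risks and costs as the formal aim. That wording is in the lay summary. The aim in section 3.1 is to determine optimal supportive care.

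**Conclusion.** The point holds in a limited form. The core list's only adverse-event outcomes depend on investigator attribution, made open-label by default, without blinded adjudication of causality and without a time window. Where a domain compares a drug arm with a cessation or no-drug arm, they do not measure the arms alike and should not be read as overall adverse-event burden. Under the assumed rates above, the attribution rule alone can produce an apparent advantage of 2.5 to 20 points for no drug when true risks are equal, and can reverse the sign of a true 20-point excess off drug. Those figures rest wholly on assumed event rates, labelling shares and 100 per arm.

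The point does not touch event-free survival, mortality, resistance or quality of life, and it does not show that the platform would miss the main harm of stopping. It is a worthwhile and cheap improvement to the outcome list, and does not invalidate the design.

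**What to change.** 1. Add to section 3.2.2 the occurrence and number of all-cause Grade 3 or higher adverse events, and of serious adverse events, from randomisation to 12 months in every arm. Make these the between-arm adverse-event comparison.
2. Keep outcomes 9 and 10 as descriptive tolerability over the same window.
3. Reconcile the recording window in section 6.2.1, which closes 30 days after the domain intervention ends and has no clear anchor in a no-drug arm, with section 4.5.5.1, which continues adverse-event review to M12 after treatment is discontinued. The window should be equal in all arms.
4. Reconcile trial treatment (6.2.1) with assigned intervention (6.3), and the 6.2.1 causality levels with the threshold in 6.1.2.

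Cost: Protocol and analysis-plan wording, some extra tables, and an adverse-event log kept open equally long in each arm. The log already takes all events with severity, so no new form is needed. The downside is that all-cause events are less specific to drug toxicity, which is the reason to keep outcomes 9 and 10 alongside them.

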4. METHODS

4.1. STUDY SETTING

This trial will be conducted by haematology or haematology/oncology units at participating hospitals in participating regions.

4.2. SELECTION OF SITES/CLINICIANS

The platform will be coordinated by the Monash University Transfusion Research Unit.

Participating sites must complete and sign a clinical trial research agreement (CTRA).

All sites participating in the platform will complete a delegation log and forward this to the Trial Management Group (TMG). Each person working on the trial must sign off a section of this log indicating their responsibilities. The TMG must be notified of any changes to trial personnel and/or their responsibilities and an updated delegation log completed.

Following substantial amendments, sites will be notified of relevant documents and training required and if and when they are able to participate in the trial.

4.3. SELECTION OF PARTICIPANTS

Patients will be considered eligible for enrolment in this platform based on eligibility criteria applied at two levels. The first level is the inclusion and exclusion criteria that determine eligibility for enrolment within the platform. Once eligible for inclusion within the platform trial, additional criteria are applied that are specific to each domain.

Patients are eligible for this trial if they fulfil all the inclusion criteria and none of the exclusion criteria in the core protocol, and the criteria for at least one of the domains.

4.3.1. Core participant Inclusion criteria

1. Aged \geq 18 years of age
2. Diagnosis of haematological malignancy, including CLL, MM or NHL
3. Eligible to receive or currently receiving Ig (IV or subcutaneous - SC Ig) replacement for history of recurrent or severe infection(s) and IgG less than the lower limit of the reference range (excluding paraprotein) OR IgG < 4g/L (excluding paraprotein)
4. Life expectancy > 12 months
5. Able to give informed consent

4.3.2. Core participant exclusion criteria

1. Treating team deems enrolment in the study is not in the best interests of the patient.

Additional eligibility criteria will apply for each domain and will be described within the relevant DSA.

4.4. CO-ENROLMENT GUIDELINES

The RATIONAL-PT platform trial seeks to evaluate supportive care interventions to prevent infection, including in therapeutic settings. Co-enrolment to other therapeutic studies is not excluded, except where these studies include interventions which might directly affect the interventions or endpoint assessments within RATIONAL-PT. In case of uncertainty, the ITSC will evaluate suitability for co-enrolment.

4.5. TRIAL PROCEDURES

4.5.1. Participant timeline

A summary of the study and follow up schedule is shown in Figure 3 and Table 1 (Schedule of Assessments).

4.5.2. Screening/recruitment

The local PI or delegate will be responsible for identifying suitable patients by reviewing the eligibility criteria and inviting them to participate in the trial.

A screening log will be completed on all patients considered for the trial including those approached but who decline to participate and ineligible patients. Patients will be screened against the eligibility

criteria outlined in this core protocol as well as those in the domain-specific appendix for which the participant is being considered.

Before commencing screening activities of patients for trial participation, consent from patients will be sought using the participant information and consent form (PICF).

All screening assessments are part of routine clinical care, therefore results from tests that are performed no more than 14 days prior to registration can be used to assess patient eligibility.

Each participant will be assigned a unique trial number when they are enrolled in the platform.

4.5.3. Treatment allocation

Participants will receive a treatment allocation after confirmation of eligibility for the Platform and at least one domain. For domains involving randomisation, randomisation will be conducted through a password-protected secure website using a central randomisation programme. Eligibility for randomisation will be assessed with reference to the inclusion and exclusion criteria and there will be no exception to eligibility requirements at the time of randomisation.

After completion of trial procedures in one domain, participants may then be eligible to rotate to a different domain. In this case, participants will re-enter the screening period at the time of informed consent to the subsequent domain. If the participant is eligible for the subsequent domain, they will be reassessed against platform criteria and then be randomised within that domain and continue to be followed according to the Schedule of Assessments.

4.5.4. Blinding

Acknowledging the difficulty in blinding to regular administration of parenteral immunoglobulin replacement, the current standard of care in many regions, treatments will be provided on an open-label basis, unless otherwise specified in the DSA. Where interventions are conducted on an open-label basis, all members of the ITSC will remain blinded to aggregate reports until a platform conclusion is reported by the DSMC.

4.5.5. Withdrawal of participants

4.5.5.1. Early withdrawal from trial

Participants should be encouraged to remain in the trial and complete continue to follow the Schedule of Assessments, including adverse events and infection review, until M12, even if they discontinue their assigned trial treatment. Participants who simply discontinue trial treatment are not considered an early withdrawal. Investigators can withdraw participants at any time if they consider this in the best interests of the participant.

Any participant withdrawn from the trial at any time, for any reason, before the last follow up visit is considered an early withdrawal. An End of Domain eCRF form is to be completed for all participants withdrawing from a domain prior to the last domain scheduled visit. Unless a participant withdraws completely (i.e. does not consent to any follow-up), participants will be followed for all adverse reactions and infectious outcomes up to 30 days after their last on-study treatment dose.

4.5.5.2. *Participants lost to follow-up*

Every effort should be made to obtain information on patients who do not attend a scheduled appointment, to obtain at least minimal efficacy and safety data (including Serious Adverse Events). A patient will be considered lost to follow-up if they miss 3 consecutive visits and cannot be contacted by the site on 3 separate, consecutive attempts (these attempts must be documented on the patient's notes).

4.5.6. *Treatment of participants*

Treatments are outlined in the relevant Domain Specific Appendices.

4.5.7. *Trial assessment schedule*

Please see Schedule of Assessments in Section 1.2.

For the purpose of scheduling and follow-up, each trial month is defined as 4 weeks (or 28 days).

4.5.8. *Assessments by visit*

The following data will be collected:

4.5.8.1. *Screening/baseline*

- Medical history, including
 - Demographics
 - Disease information
 - Disease-specific therapy, including:
 - Prior anticancer therapy for the underlying malignancy
 - Prior additional steroid use for the underlying malignancy in the prior 12 months to screening
 - Concomitant medications (ALL) (including vaccinations, and current, ongoing anticancer therapy)
 - Covid-19 vaccination history
 - Pneumococcal antibody response (if available)
 - Infection history for the 12 months prior to screening

- ECOG Performance Status
- Haematology – FBE, lymphocyte subsets by flow cytometry (if available)
- Biochemistry – Renal function tests (Electrolytes and creatinine) and liver function tests (includes Bilirubin, ALT and ALP), IgG
- Quality of life (EQ-5D-5L, EORTC QLQ-C30 & FACT-N)

4.5.8.2. Day 1

- ECOG Performance Status
- Concomitant medications (ALL)
- Ig levels (trough if on 4-weekly IVIg, steady-state if on SC Ig)
- Safety monitoring
- Infectious event details
- Biobank sub-study only
 - Peripheral blood (whole blood and serum) for correlative studies, including COVID-19 anti-spike protein levels.
 - Faecal sample

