4.6. OUTCOME ADJUDICATION COMMITTEE (OAC)

An independent outcome adjudication committee, comprising of infectious disease experts and haematologists, will be established. The OAC will be responsible for reviewing and adjudicating on: grade of all infection outcomes, time of major infections; clinically documented infections; microbiologically documented infection; susceptibility profile of microbiologically documented infections and infection-related mortality.

The OAC will be provided with the details of all infectious events. Details will be provided in a blinded fashion, to ensure that the OAC are not aware of which treatment arm the participant was receiving. Committee members will individually assess the events according to the secondary outcomes as outlined above. All members will subsequently participate in a series of teleconferences for final consensus decision on the primary and secondary end-points for each trial patient.

5. Statistical Methods

Summary statistics, analyses and data visualisations will be generated using R version 4.0.0 or later or documented procedures in SAS (9.4 or later) or Stata (V. 17 or later) as appropriate. A detailed

description of the trial estimands, approaches to reporting, statistical models, adaptations and decision criteria, and justification of the trial design by simulation are presented in the Master Statistical Analysis Appendix to the Core Protocol and the Domain-specific Statistical Analysis Plans (SAPs). A Simulations Appendix will be updated periodically as an operational document which will contain the results of Monte Carlo simulations that are conducted to demonstrate and understand the operating characteristics of a domain or comparison of interest, across a range of plausible assumptions regarding the outcome rates, treatment effects, and recruitment rates.

The RATIONAL-PT has an adaptive platform design which means that it does not have a fixed sample size that determines when the study will end. Individual domains may have fixed caps on sample size as described within their DSAs.

The primary analysis will be a standalone analysis of each comparison within each domain of the RATIONAL-PT.

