6.3.3. Investigator responsibilities

All SAEs must be assessed by, and reports signed, by an Investigator.

It will be left to the investigator's clinical judgment whether or not an adverse reaction is of sufficient severity to require that the participants should be discontinued from the treatment. A participant may also voluntarily withdraw from treatment due to what they perceive as an intolerable adverse event. If either of these occurs, it must be made clear if the participant is being withdrawn from the trial or just the trial intervention.

The Investigator is responsible for reporting SUSARs arising at their site, Significant Safety Issues (SSIs) and Urgent Safety Measures (USMs) to their Institution.

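### Section 4.5.5.1 ends outcome collection early for participants withdrawn from the trial who have not refused all follow-up, so their 12-month infection and mortality outcomes can be unknown

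*Protocol*

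**What the plan says.** Section 4.5.5.1 of the protocol separates two groups.

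- **Treatment stopped only.** These participants are encouraged to keep to the Schedule of Assessments until M12. The section adds: "Participants who simply discontinue trial treatment are not considered an early withdrawal".
- **Withdrawn from the trial.** This covers any reason and any time before the last follow-up visit. The investigator may also initiate it: "Investigators can withdraw participants at any time if they consider this in the best interests of the participant". Unless the person refuses every form of follow-up, "participants will be followed for all adverse reactions and infectious outcomes up to 30 days after their last on-study treatment dose".

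Section 6.3.3 asks sites to say which group applies when an adverse reaction or event ends treatment: "it must be made clear if the participant is being withdrawn from the trial or just the trial intervention".

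The outcomes run longer than the 30-day rule. EFS in section 3.2.1 runs "until occurrence of a Grade 3 or higher infection (as defined by CTCAE Version 5), or death from any cause", with no fixed horizon. Section 3.2.2 includes "Occurrence of at least 1 Grade 3 or higher infection(s) from randomisation to 12 months" and "All-cause mortality at 12 months", together with infection-related mortality at the same time point. Section 4.5.7 sets a trial month at 28 days. Section 4.5.4 makes treatment open-label unless a Domain-Specific Appendix (DSA) says otherwise.

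**The concern.** The 30-day rule is more than a safety window, because it names infectious outcomes, which are the efficacy outcomes of this platform. The adverse event log has its own 30-day window in section 6.2.1. The core protocol therefore ends efficacy follow-up for some people who have not refused it. It does not name vital status for them, although death is part of the primary outcome. Section 6.3.2 covers deaths on trial, and nothing there extends to deaths after withdrawal and after the window.

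Two things are at stake. The first is information: an analysis plan can model missing data but cannot restore data that the protocol did not ask sites to collect. The second is possible bias. If withdrawal is related to infection risk and differs between arms, which open-label treatment allows, the missing follow-up is informative.

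**Working it through.** The protocol gives no withdrawal rate, event rate or sample size tied to this rule, so there is no stated figure to reproduce. The check has two parts: how much time is lost per person, and how many events that could mean.

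**1. When collection ends**

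Count days from D1 (day 0). With 28-day months (section 4.5.7), M12 is day 12 x 28 = 336. Any gap between randomisation and D1 is set by the DSA and is ignored here. Let d be the day of the last dose and w the day of withdrawal. A person who has stopped treatment stays on the schedule until w, so

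collection ends at c = min(max(w, d + 30), 336), and days lost = 336 - c.

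The loss is largest when w is no later than d + 30. It is then max(0, 336 - (28k + 30)) for a last dose at month k:

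| Last dose | Window closes (day) | Most days lost | Share of 336 |
|---|---|---|---|
| M1 | 58 | 278 | 83% |
| M3 | 114 | 222 | 66% |
| M6 | 198 | 138 | 41% |
| M9 | 282 | 54 | 16% |
| M11 | 338 | 0 | 0% |

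These are maxima. Take someone who stops treatment at M3 (day 84) and is withdrawn at M6 (day 168). The window closed on day 114, but the schedule applied until day 168. The rule asks for nothing after withdrawal, and the loss is 336 - 168 = 168 days, not 222.

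**2. Share of EFS events missed**

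Assumptions, none of them from the document:

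- a share a of all participants is withdrawn but can still be followed;
- withdrawal is unrelated to risk;
- event times are exponential, with a risk of 15%, 25% or 40% by day 336;
- the last dose is uniform over days 28-308.

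With S(t) = (1 - risk)^(t/336), the share of all EFS events by M12 that is missed is

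a x F, where F = mean of [S(c) - S(336)] / [1 - S(336)].

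Single cases at 25% risk show the scale:

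- Last dose at M3, withdrawn by day 114: S(114) = 0.75^(114/336) = 0.907, so (0.907 - 0.750)/0.250 = 0.63 of that person's expected events are missed.
- Stop at M3, withdrawn at M6: S(168) = 0.75^0.5 = 0.866, so (0.866 - 0.750)/0.250 = 0.46.

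Averaged over last-dose timing:

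| Timing of withdrawal | F at 15% / 25% / 40% risk | Missed at a = 5% | Missed at a = 10% |
|---|---|---|---|
| Within 30 days of last dose (maximum) | 0.396 / 0.384 / 0.364 | 1.8-2.0% | 3.6-4.0% |
| Uniform between last dose and M12 | 0.227 / 0.218 / 0.203 | 1.0-1.1% | 2.0-2.3% |

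Last-dose timing matters too. For the maximum case at a = 10%, the figure is 5.6-6.0% if last doses fall over days 28-168 and 1.7-1.9% if they fall over days 168-308.

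**The case against.** The strongest reply is that the group is narrow by design. Section 4.5.5.1 tells sites to keep people in the trial after treatment stops, and section 4.5.8.3 allows telehealth in place of clinic visits. Someone content to be followed to M12 can normally stay in. Those left are people who ask to leave but tolerate some follow-up, and people withdrawn by the investigator. Not refusing all follow-up is not the same as agreeing to follow-up until M12, and the consent wording is not shown. A DSA could also extend follow-up. All of this stands. It limits the size of the point, but no sentence of the core protocol removes the 30-day rule.

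A reader might also infer more than the text supports:

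- **That everyone who stops treatment is lost after 30 days.** Treatment discontinuers stay on the schedule to M12.
- **That EFS in this group is always cut off at a date fixed by the last dose.** For late withdrawals, collection runs to the withdrawal date. How EFS is then censored belongs to analysis documents that are not shown.
- **That section 4.6 contradicts the rule**, because the adjudication committee is to reach a "final consensus decision on the primary and secondary end-points for each trial patient". That sentence describes how events are adjudicated and does not promise complete 12-month data.
- **That the treatment comparison is biased.** This needs withdrawal to depend on risk and to differ by arm. The protocol gives no evidence on either.

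**Conclusion.** The point holds in a limited form. For participants withdrawn from the trial who have not refused all follow-up, the core protocol requests no infection or survival data after the later of withdrawal and 30 days after the last dose. Their 12-month outcomes can be unknown unless already determined by an earlier event, and EFS follow-up ends early.

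The size is modest under the stated assumptions: about 0.20-0.23 x a of EFS events by M12 with withdrawal spread between last dose and M12, and at most 0.36-0.40 x a with withdrawal within 30 days of the last dose. If withdrawal is unrelated to risk, the cost is lost information only. If it is related to risk and differs by arm, bias can follow, but the document does not allow its size to be stated. People who refuse all follow-up are outside this point, since no rule recovers their data. This is a worthwhile low-cost improvement and not a flaw that undermines the design.

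**What to change.** In section 4.5.5.1, replace the 30-day limit on outcome follow-up with wording such as:

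> Unless refused, and within the consent that remains, withdrawn participants are followed for infectious outcomes (including Grade 3 or higher infection), hospitalisation and vital status until the scheduled M12 date by phone or medical record, regardless of treatment received; refusal of visits is recorded separately from refusal of further data collection.

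Leave the adverse event log window in section 6.2.1 unchanged. If a DSA already extends follow-up, align the two texts.

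The cost is a formal amendment agreed by the International Trial Steering Committee and approved by the ethics committee (section 7.3), a possible revision of the consent form, one data field for the level of withdrawal, and a few phone or record checks per withdrawn participant. No additional participants are needed. The change helps only follow-up that is still to come, so it is best made early.
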